## **4. TREATMENT**

### **4.1. Treatment Schedule**

Patients should start axitinib treatment on day 1, week 1 of the study and continue for 8 weeks.

Patients will be prescribed 1 pack (28 tablets) of 5mg BID at week 1. Patients will then be prescribed further axitinib every 2 weeks following the dose modification schedule detailed in

section 4.2 (depending on toxicities and blood pressure). Doses should be taken appropriately 12 hours apart and patients should be instructed to take their doses at approximately the same time each day with or without food as per instruction. On clinic days only, patients will be advised to fast for 6 hours prior to their clinic visit.

Patients should be advised to stop axitinib treatment a minimum of 36 hours and maximum of 7 days prior to week 9 surgery and tissue collection.

If a patient vomits or misses a dose, an additional dose should not be taken. The next prescribed dose should be taken at the usual time. If the patient reports having missed a dose or vomiting, this should be recorded in the source documents and case report forms (CRFs).

#### 4.2. Dose Modifications

Dose Level	Dose	Dispensed As
+2	10mg BID	2 x 5mg tablets BID (2 x 5mg packs)
+1	7mg BID	1 x 5mg tablet BID + 2 x 1mg tablets BID (1x 5mg + 2 x 1mg packs)
0 (starting dose)	5mg BID	1 x 5mg tablet BID (1 x 5mg pack)
-1	3mg BID	3 x 1mg tablets BID (3 x 1mg packs)
-2	2mg BID	2 x 1mg tablets BID (2 x 1mg packs)

#### Dose Escalation

Patients who tolerate axitinib with no adverse events related to study drug above CTCAE grade 2 for a consecutive 2 week period should follow the aggressive dose escalation schedule above and have their dose increased by one dose level to a maximum of 10 mg BID. The only exception to this would be if the patient's blood pressure (BP) is >150/90 mm Hg or the patient is receiving antihypertensive medication. If the patient is receiving antihypertensive medication and a dose escalation is clinically indicated this should be considered by the onsite clinical team.

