## 3. TRIAL DESIGN

### 3.1. General Design

NAXIVA is a single arm, single agent, open label, phase II feasibility study of axitinib in patients with both metastatic and non-metastatic renal cell carcinoma of clear cell histology. 20 patients will be recruited from multiple centres within the United Kingdom.

Patients who have signed informed consent and who have met all eligibility criteria will be registered into the trial.

The starting dose of axitinib will be 5mg BID and escalated to 7mg BID and then 10mg BID. A dose modification assessment will take place every 2 weeks in clinic during the 8 week pre-surgical treatment period and will be dependent on tolerability of treatment. Patients will follow an aggressive axitinib dose escalation process within the 8 week period to a maximum of 10mg BID. Patients should stop axitinib a minimum of 36 hours and a maximum of 7 days prior to surgery in week 9.

Blood, urine and tissue samples will be taken prior to and during therapy to evaluate biomarkers of treatment response. Nephrectomy and IVC tumour thrombectomy will be planned for all patients on the trial.

Response to axitinib in VTT, primary tumour and any RECIST measureable lesion will be correlated with changes in molecular markers.

Patients will be followed up in clinic at 6 & 12 weeks post surgery.

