#### Dose Interruption and Reduction

Patients experiencing non-haematological drug reactions greater than CTCAE Grade 2 or haematological reactions greater than CTCAE Grade 3 should undergo dose modification. The current version of the Summary of Product Characteristics (SmPC) should be used to assess whether any adverse event is attributable to the drug.

Axitinib should be stopped in the event of significant toxicity and restarted if appropriate when toxicities have resolved. If the patient has had an interruption of axitinib more than 2 weeks, it must be discussed with the Chief Investigator (CI) before the patient restarts study drug.

Patients permanently removed from treatment for intolerable toxicity should receive a post treatment CT scan assessed according to RECIST 1.1 criteria, and should revert to standard of care.

The criteria for dose modification for axitinib related adverse events are summarised in the table below:

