#### Criteria for dose modification for axitinib- related adverse events (other than hypertension or proteinuria)

Related Adverse Events	Intervention
Any grade: bleeding where medical	Temporarily interrupt the axitinib dose.

intervention is required		
Any grade: posterior reversible encephalopathy syndrome (PRES)		Patients with signs or symptoms should temporarily interrupt or permanently discontinue axitinib treatment. In case of severe or persistent arterial hypertension and symptoms suggestive of posterior reversible encephalopathy syndrome, a diagnostic brain magnetic resonance image (MRI) should be considered. If PRES is confirmed, the patient should permanently discontinue axitinib.
Grade 1		Continue at same dose level
Grade 2		Continue at same dose level
Grade $\geq 3$ non-haematologic treatment-related toxicity or Grade 4 haematologic toxicity (other than those below)		Interrupt dosing; re-start at one lower dose level as soon as improvement to CTCAE Grade $\leq 2$ . If patient requires dose reduction below 2mg BID, contact SCTR for discussion prior to implementation.
Grade 4 lymphopaenia		Continue at the same dose level at the discretion of the investigator.

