#### **Dose re-escalation**

Re-escalation back to the previous dose level is permitted in the absence of grade ≥3 haematologic or grade ≥2 non-haematologic treatment-related toxicity in the previous 4 weeks of treatment.

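### Protocol 4.2 has two different rules for raising the dose after a reduction and does not say which prevails; its grade 1–2 table rows are also unclear about escalation

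*Protocol*

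**What the plan says.** Four parts of Protocol 4.2 bear on whether a patient's dose goes up, stays or comes down.

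- **Dose Escalation.** The rule covers "Patients who tolerate axitinib with no adverse events related to study drug above CTCAE grade 2 for a consecutive 2 week period". Such patients should "have their dose increased by one dose level to a maximum of 10 mg BID". The exception is a closed one: "The only exception to this would be if the patient's blood pressure (BP) is >150/90 mm Hg", or the patient is on antihypertensive medication, in which case the site team decides.
- **Dose Interruption and Reduction.** The threshold for action is set as follows: "Patients experiencing non-haematological drug reactions greater than CTCAE Grade 2 or haematological reactions greater than CTCAE Grade 3 should undergo dose modification".
- **Adverse-event table under that heading** (hypertension and proteinuria are handled separately). The rows for grade 1 and for grade 2 both read "Continue at same dose level".
- **Dose re-escalation.** "Re-escalation back to the previous dose level is permitted in the absence of grade ≥3 haematologic or grade ≥2 non-haematologic treatment-related toxicity", with a look-back of four weeks of treatment.

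Protocol 3.1 sets the intent: "Patients will follow an aggressive axitinib dose escalation process within the 8 week period to a maximum of 10mg BID", with an assessment every two weeks. No sentence ranks these rules against each other.

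**The concern.** The main problem is the patient whose dose has already been reduced. Dose Escalation refers to the dose-level table at the start of 4.2, which includes the two levels below the starting dose. A reduced patient is therefore on that schedule, and nothing in the paragraph takes them off it. Dose re-escalation then sets a different test for what may be the same upward step, with a longer look-back and a lower non-haematologic threshold.

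Such a patient is foreseeable. The adverse-event table restarts dosing one level lower as soon as toxicity has improved to grade 2 or below, so restarting with residual grade 2 toxicity is within the plan.

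The secondary problem is the never-reduced patient with grade 1 or 2 events. A site that applies the table rows as written would hold the dose where Dose Escalation directs an increase.

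Both affect how toxicity is managed and how much drug is given. Delivered dose is also reported: total dose in Protocol 9.2 (Final Analysis), total dose and the numbers of escalations and reductions in SAP 7.4, and a correlation of total dose with the percentage reduction in venous tumour thrombus in SAP 7.7. In a trial of 20 patients at 7 sites, differences in site practice would enter those summaries.

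**Working it through.** The plan states no figure that this point could reproduce. The check sets the rules side by side and then adds up the planned dose.

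**1. Rules for a previously reduced patient** (blood pressure acceptable, no antihypertensives)

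| Related toxicity since the reduction | Dose Escalation | Dose re-escalation |
|---|---|---|
| Grade 1 only, any type | Raise after 2 weeks | Permitted after 4 weeks |
| Grade 2 haematologic | Raise after 2 weeks | Permitted after 4 weeks |
| Grade 2 non-haematologic, persisting | Raise after 2 weeks | Not permitted |
| Grade 3 or above | Do not raise | Not permitted |

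In the first two rows only the timing differs. In the third row the instructions are opposite.

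**2. Dose per two-week block**

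Protocol 3.1 and 4.1 give two doses a day, two-weekly assessments and eight weeks of treatment, so there are four blocks of 14 days. Dose per block = mg per dose × 2 × 14:

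- 3 mg BID: 3 × 28 = 84 mg
- 5 mg BID: 5 × 28 = 140 mg
- 7 mg BID: 7 × 28 = 196 mg
- 10 mg BID: 10 × 28 = 280 mg

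**3. Patient reduced to 3 mg BID at week 3** (assumed path; full compliance, no interruption)

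- Dose Escalation, 5/3/5/7 mg BID: 140 + 84 + 140 + 196 = 560 mg.
- Dose re-escalation, grade 1 events only after the reduction, 5/3/3/5 mg BID: 140 + 84 + 84 + 140 = 448 mg. This is 448/560 = 0.80, or 20% less.
- Dose re-escalation, persisting grade 2 non-haematologic toxicity, 5/3/3/3 mg BID: 140 + 84 + 84 + 84 = 392 mg. This is 392/560 = 0.70, or 30% less.

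**4. Never-reduced patient with continuing grade 1–2 events**

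- Dose Escalation, 5/7/10/10 mg BID: 140 + 196 + 280 + 280 = 896 mg.
- Table rows read literally, 5/5/5/5 mg BID: 4 × 140 = 560 mg. This is 560/896 = 0.625, or 37.5% less.

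Dose re-escalation does not apply to this patient.

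**5. Can the four-week window be met?**

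The nominal dispensing days are 1, 15, 29 and 43 (weeks 1, 3, 5 and 7), and treatment ends on day 56.

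- Toxicity at 10 mg BID: this dose is first given on day 29, and 29 + 28 = 57, which is after the course ends. A return to 10 mg BID cannot be reached.
- Toxicity at 7 mg BID: this dose is first given on day 15, and 15 + 28 = 43. The last dispensing visit is met only if the event falls on day 15 itself.
- Toxicity at 5 mg BID on days 1–14: adding 28 gives days 29–42, before the day 43 visit. The window can be met.

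The seven-day visit windows could move these days, and a dose interruption would delay them.

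**The case against.** **The specific rule displaces the general one.** Dose re-escalation has its own heading and covers only a return to a previous level, so many readers would let it govern reduced patients. That is a reasonable reading, but the protocol does not state it, and Dose Escalation describes its own exception as the only one. The objection makes the conflict easier to resolve; it does not remove it.

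**The table concerns reductions only.** It sits under Dose Interruption and Reduction, whose threshold for action is above grade 2 for non-haematologic and above grade 3 for haematologic reactions. In that setting, staying at the same level most naturally means that no reduction is needed. Reading it as a bar on escalation would leave the grade 2 threshold in Dose Escalation with little effect and would cut against the rapid escalation intended in Protocol 3.1. Most of this objection stands, which is why the point is secondary. It does not settle the matter, because 4.2 as a whole is titled Dose Modifications and includes escalation, and Protocol 3.1 and 4.1 use the term in that wider sense.

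**A three-way contradiction.** A reader might infer that any patient with a grade 1–2 event is told to go up, to stay and not to re-escalate. The documents do not support that. Dose re-escalation applies only after a reduction, and it does not bar patients with grade 1 events or grade 2 haematologic events. Where it does bar the step, it agrees with staying at the same dose.

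**The timing.** A permissive rule that can seldom be used contradicts nothing, and it is usable after an early reduction from 5 mg BID. What remains is a question about what was intended.

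**Conclusion.** The inconsistency is real, and it is clearest for previously reduced patients. With persisting grade 2 non-haematologic toxicity the two paragraphs give opposite instructions (560 mg against 392 mg planned). With grade 1 events only they differ in timing (560 mg against 448 mg). The table wording for never-reduced patients is a weaker ambiguity: 896 mg against 560 mg, but only on the less natural, literal reading. The four-week window rules out a return to 10 mg BID on nominal visit days, but not every re-escalation.

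These totals assume full compliance, 56 days of treatment, no interruption and no blood-pressure exception. They illustrate single patients; they do not estimate a trial average. The documents do not say how many patients would be affected: the phase II summary in Protocol 1.4.1 groups its most frequent events as grades 1–4, with no separate grade 1–2 share.

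A reader might also infer that the trial result could not be attributed to the stated regimen. That goes too far. Dosing depends on tolerability by design, escalation details are collected (Protocol 8.1), delivered dose is reported, and the requirement of at least 3 improvements is unchanged. What is at stake is consistent patient handling and the interpretation of the dose summaries and the dose–response correlation.

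**What to change.** The clinical team must reconcile Dose Escalation, the grade 1–2 rows of the adverse-event table and Dose re-escalation. Each patient state (never reduced or previously reduced, by grade and by haematologic or non-haematologic event) should have one instruction. A single table in 4.2 would do this. The text should state:

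1. whether Dose Escalation applies after a reduction or is replaced by Dose re-escalation;
2. what the grade 1 and grade 2 rows mean for a patient otherwise due to escalate;
3. whether the four-week window is meant to be usable within the eight-week course.

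This review does not propose a dose or threshold, or say which passage should prevail. The cost is a wording amendment to 4.2 and a note to sites, with no extra patients, visits or procedures.

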#### Dose Interruption and Reduction

Patients experiencing non-haematological drug reactions greater than CTCAE Grade 2 or haematological reactions greater than CTCAE Grade 3 should undergo dose modification. The current version of the Summary of Product Characteristics (SmPC) should be used to assess whether any adverse event is attributable to the drug.

Axitinib should be stopped in the event of significant toxicity and restarted if appropriate when toxicities have resolved. If the patient has had an interruption of axitinib more than 2 weeks, it must be discussed with the Chief Investigator (CI) before the patient restarts study drug.

Patients permanently removed from treatment for intolerable toxicity should receive a post treatment CT scan assessed according to RECIST 1.1 criteria, and should revert to standard of care.

The criteria for dose modification for axitinib related adverse events are summarised in the table below:

#### Criteria for dose modification for axitinib- related adverse events (other than hypertension or proteinuria)

Related Adverse Events	Intervention
Any grade: bleeding where medical	Temporarily interrupt the axitinib dose.

intervention is required		
Any grade: posterior reversible encephalopathy syndrome (PRES)		Patients with signs or symptoms should temporarily interrupt or permanently discontinue axitinib treatment. In case of severe or persistent arterial hypertension and symptoms suggestive of posterior reversible encephalopathy syndrome, a diagnostic brain magnetic resonance image (MRI) should be considered. If PRES is confirmed, the patient should permanently discontinue axitinib.
Grade 1		Continue at same dose level
Grade 2		Continue at same dose level
Grade $\geq 3$ non-haematologic treatment-related toxicity or Grade 4 haematologic toxicity (other than those below)		Interrupt dosing; re-start at one lower dose level as soon as improvement to CTCAE Grade $\leq 2$ . If patient requires dose reduction below 2mg BID, contact SCTR for discussion prior to implementation.
Grade 4 lymphopaenia		Continue at the same dose level at the discretion of the investigator.

### Axitinib dose reduction guidance for hypertension

Degree of Blood Pressure Elevation		Management	
Systolic Pressure		Diastolic Pressure	
2 consecutive BP readings show systolic pressure $> 150$ mmHg	OR	2 BP readings separated by at least 1 hour show diastolic pressure $> 90$ mmHg	If not on maximal antihypertensive treatment, institute new or additional antihypertensive medication and maintain dose of axitinib. If on maximal antihypertensive treatment, reduce axitinib to one lower dose level.
2 consecutive BP readings show systolic pressure $> 160$ mmHg	OR	2 BP readings separated by at least 1 hour show diastolic $> 100$ mmHg	Interrupt dosing *; adjust antihypertensive medication; as soon as BP is less than 150/90 mmHg, restart axitinib at one lower dose level.
Recurrent hypertension following previous dose reduction (2 consecutive BP readings show systolic pressure $> 150$ mmHg)	OR	Recurrent dBP $> 90$ mmHg (2 BP readings separated by at least 1 hour) following previous dose reduction.	Repeat axitinib dose reduction by one lower dose level. If a patient requires dose reduction below 2 mg BID, contact SCTR for discussion.

\* If dose is interrupted, patients receiving antihypertensive medications should monitor closely for hypotension.

### Axitinib Dose reduction for Proteinuria

- If dipstick shows  $\geq 2$  proteinuria, perform 24 hour urine collection or urinary protein:creatinine ratio (PCR). Dosing may continue while waiting for test results.
- If  $< 2$  g proteinuria/24 hour or urinary PCR  $< 200$  mg/mmol is reported, continue dosing at the same dose level.
- If  $\geq 2$  g proteinuria/24 hours or urinary PCR  $\geq 200$  mg/mmol is reported, withhold dose and repeat 24 hour urine collection or urinary PCR (interval at investigator discretion) until proteinuria is  $< 2$  g/24 hours or urinary PCR  $< 200$  mg/mmol. Restart axitinib at

the same dose or one lower dose level at discretion of the investigator. Monitor renal function in accordance with standard practice.

#### **Dose re-escalation**

Re-escalation back to the previous dose level is permitted in the absence of grade ≥3 haematologic or grade ≥2 non-haematologic treatment-related toxicity in the previous 4 weeks of treatment.

#### **Axitinib dose interruption for surgery or surgical procedures**

If major surgery or an interventional procedure (e.g. endoscopy) which is not part of NAXIVA study is required, treatment with axitinib must be interrupted a minimum of 36 hours and a maximum of 7 days before the procedure and the patient's blood pressure should be monitored closely for hypotension. Patients may resume axitinib seven days after minor surgery and 2-3 weeks after major surgery, assuming the wounds have completely healed. The decision to resume axitinib therapy after surgery should be based on clinical judgment of adequate wound healing.

#### **4.3. Duration of Treatment**

Treatment with study drug should be discontinued if it is considered to be in the best interest of the patient. Reasons for treatment discontinuation include:

- Disease progression
- Occurrence of intolerable side effects
- Pregnancy
- Patient withdrawal of consent or non-compliance

#### **4.4. Concomitant Therapy**

Axitinib is metabolised primarily by liver enzymes, in particular CYP3A4. All medication considered necessary for the patients' welfare and which is not expected to interfere with the evaluation of the study drug may be given at the discretion of the investigator. Concomitant medications must be recorded in the patients' source documentation, as well as the appropriate pages of the CRF.

Contraindicated concurrent medications include:

Agents known to induce CYP3A4 or CYP1A2 including but not limited to:	Agents known to inhibit CYP1A2, CYP2C19 or CYP3A4 including but not limited to:

 
○ Amobarbital,
 
○ Carbamazepine,
 
○ Dexamethasone,
 
○ Felbamate,
 
○ Nevirapine,
 
○ Omeprazole,
 
○ Phenobarbital,
 
○ Phenytoin,
 
○ Primidone,
 
○ Rifabutin,
 
○ Rifampicin,
 
○ St John's wort
 
	
 
○ Amitriptyline
 
○ Amprenavir,
 
○ Artemisinin,
 
○ Atazanavir,
 
○ Atazanavir,
 
○ Cimetidine,
 
○ Ciprofloxacin,
 
○ Clarithromycin,
 
○ Delavirdine
 
○ Enoxacin,
 
○ Erythromycin,
 
○ Ethinyl,
 
○ Fluvoxamine,
 
○ Fosamprenavir
 
○ Grapefruit juice,
 
○ Imipramine
 
○ Indinavir,
 

	
 
 Itraconazole,
 
 Ketoconazole,
 
 Lopinavir,
 
 Mexiletine,
 
 Miconazole,
 
 Nelfinavir,
 
 Ritonavir,
 
 Saquinavir,
 
 Tacrine,
 
 Telithromycin,
 
 Thiabendazole,
 
 Ticlopidine.
 
 Verapamil,
 
 Zileuton
 

--	--

- Other approved or investigational systemic anticancer treatments, including chemotherapy, hormone therapy and immunotherapy.
- Other investigational drugs.

The use of potent antacids such as proton pump inhibitors (except those listed above) and histamine H2 antagonists is permissible, if medically necessary. However, patients requiring chronic antacid therapy should avoid their use for 2 hours before and for 2 hours after taking axitinib tablets.

The contraindicated medications detailed above may only be used in exceptional circumstances and following written confirmation from SCTR U of the CI's approval.

The current version of the SmPC should be used to assess whether any other concomitant medications are permissible.

Other supportive medicines such as thyroid replacement therapy, anti-emetics and anti-diarrhoeal medicines are permitted in accordance with local practice.

#### **4.5. Compliance with Treatment**

The study drug must not be used outside the context of the NAXIVA protocol.

Patients must be asked to bring all their trial medication every time they attend the clinic for the purposes of treatment compliance assessment and drug accountability. Every effort should be made to encourage patients to return the unused medication and empty packs. The unused tablets should be collected by the investigator/study nurse and counted to ascertain patient compliance, medication will then be returned to pharmacy for drug accountability prior to destruction according to local practices. Drug accountability and destruction records should be maintained by the local pharmacy.

#### **4.6. Drug Supplies and Labelling**

##### **Drug Supply**

Axitinib is supplied free of charge by Pfizer to Tayside Pharmaceuticals as 1mg and 5mg immediate release film-coated tablets and supplied in blister packs. Each 1mg and 5mg carton will contain 56 tablets (four blister sheets of 14 tablets per pack).

Tayside Pharmaceuticals will repack 2 intact blister sheets of 14 tablets each into a new carton along with the patient information leaflet (PIL) for each strength of axitinib. Each carton will then be labelled as per approved label. Release of the re-packaged drug will be carried out by a Qualified Person (QP) at Tayside Pharmaceuticals. IMP will then be dispatched to sites. The schedule of responsibilities for this arrangement is detailed in the contract between Tayside Pharmaceuticals and the sponsor.

SCTRUM will arrange for a supply of axitinib to be sent from Tayside Pharmaceuticals to the relevant pharmacy department following centre initiation. Local R&D approval and a study agreement must be in place before any drug can be shipped to sites.

Sites will receive an initial supply of axitinib after completion of site initiation. Each site will receive; 2x 5mg pack as a starting dose and 3x 1mg packs of axitinib to cover any unexpected dose adjustments within the first 2 weeks of the patient schedule.

SCTRUM will closely monitor axitinib supply at sites however sites will be expected to notify SCTRUM when stock is required as per the NAXIVA Pharmacy Manual. A trial specific order form will be included in the pharmacy pack. Sites must have a minimum of 1x 5mg pack and 3x 1mg packs of axitinib in stock during the recruitment period.

